## INTRODUCTION & RATIONALE

Scleral lens (SL) prescribing has dramatically increased over the past few years likely because of the advent of better SL designs, better materials, and greater awareness of the technology. SL market growth has also likely increased because SLs were once reserved for patients with complex ocular surface diseases, though advances with SL technologies have allowed SL fitting to include patients with dry eye and even patients who have relatively uncomplicated refractive errors. While SLs are maintained and cared for much like soft contact lenses (e.g., they require a contact lens care system), SL wearers also need help with applying their lenses. Patients specifically are advised by their care provider to insert their SLs with their fingers (tripod method), a DMV inserter with an open or closed end (hole potentially aides in vision), or a specialized o-ring that is balanced on a finger. Our clinic also utilizes a tea light candle with a DMV inserter attached to the top of it when patients have mobility issues. While work from this investigator's study group has found that 54% of patients prefer DMV inserters for applying their SLs as compared to the above other options, these preliminary data were obtained through a cross-sectional electronic survey from subjects who completed their SL fitting up to two years ago. Therefore, the goal of this proposal is to conduct a randomized controlled study aimed at learning the best method for applying SLs and factors associated with successfully completing SL application and removal training. These data are needed because it will help practitioners with patient education and because it may increase the likelihood that patients will be successful with SLs.

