## STUDY DESIGN

### *Subjects and Recruitment*

This study will be conducted at the UAB School of Optometry (Birmingham, AL, USA). Subjects will be recruited by word of mouth during regular clinical care. Adult (>18 years) subjects will be recruited for this study. Subjects will be excluded if they have past experience or advanced knowledge of SLs, a physical or cognitive condition that may prevent them from successfully wearing SLs (e.g., stroke), or if they are currently participating in another clinical trial. Since there is limited data on this topic and since the literature lacks a method for calculating a sample size for a five-way comparison, a true sample size calculation is not possible for this project. Since this study is preliminary in nature, 25 subjects will be recruited to gain an initial understanding of how subjects prefer to apply SLs. Five additional subjects will be recruited to account for screen failures (total of 30 subjects).

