**4. Randomization:** The investigator will access the online randomization tool (REDCap) and determine the order by which subjects will apply their lenses (*DMV inserter with an open end (A), DMV inserter with a closed end (B), three fingers (C), o-ring (D), tea light candle (E)*). Right eyes will undergo the application protocol; however, if the patient only needs a SL for their left eye, the left eye will undergo the protocol. Hand and eye dominance will be recorded. Subjects will then be instructed via training videos created by the investigators on how to do each application method. Each training video will be shown before starting each application method, and the examiner will answer the subject's questions prior to attempting the application method. The same investigator will teach each subject. Subjects will be timed during each application; however, time recording will not be made obvious. After a subject successfully completes an application method once for the designated eye, they will be asked to do the subsequent method. If a subject is unsuccessful with a method and declines to continue that method after being encouraged, the time will be recorded, and they will be allowed to try the next method. The subject will be allowed up to 15 minutes to complete each method. If the subject is unable to complete the method within that time frame, they will be instructed to do the next method to help avoid fatigue. If a patient stops a procedure before completing an application, this event will be recorded. Patients will be encouraged to try all five methods on the same day; however, subjects will be allowed to come back on a subsequent day if they get tired. Subjects will be asked to rank the ease of application for each method from easiest to most challenging after trying each method. If a subject needs a SL for their contralateral eye, they will be taught how to apply this lens after they have completed the training for their designated eye. If a subject is able to apply the lenses, they will be asked to remove the lenses as well. Only one removal method will be used (small plunger), and the removal time will also be timed for each method (timed separately from application).

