#### Data Collection and Analysis

Data collection will be performed with Research Electronic Data Capture (REDCap). Data will be analyzed with STATA 16 (StataCorp LLC; College Station, TX). Means and standard deviations will be used to understand general data trends. ANOVA will be used when comparing application methods. Regression analysis will be used to find associations with the speed of being able to complete the application process. Paired t-tests will be used to compare questionnaire scores at the final visit to the baseline visit. If the assumptions of these tests cannot be met, suitable alternative statistical tests (e.g., Kruskal-Wallis) will be used.

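### Unsuccessful attempts are recorded, but the plan compares no success rates between methods and gives no rule for give-up or 15-minute times in a per-method time comparison

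*Combined protocol and SAP*

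**What the plan says.** The Introduction and Rationale sets two goals: learning which application method is best, and learning "factors associated with successfully completing SL application and removal training".

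Under Visit 2, step 4 (Randomization), every subject tries all five methods. The online tool is used to "determine the order by which subjects will apply their lenses", so the comparison is within subject. Each attempt is timed and can end in three ways:

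- The subject succeeds once and moves on.
- The subject gives up: "If a subject is unsuccessful with a method and declines to continue that method after being encouraged, the time will be recorded".
- The 15-minute allowance runs out and the subject moves to the next method.

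The same step adds: "If a patient stops a procedure before completing an application, this event will be recorded". Subjects also rank the methods by ease.

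The Data Collection and Analysis section says "ANOVA will be used when comparing application methods" without naming the outcome. It adds regression on speed of completion, paired t-tests on questionnaires, and a general fallback with Kruskal-Wallis as the example. It names no success outcome, no method for binary data, and no rule for the time of an unsuccessful attempt.

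**The concern.** A time from a successful attempt says how long the method took. A time from an abandoned attempt says how long the subject persisted. The two are not on one scale, and the plan does not say how to keep them apart.

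An analyst with these data and this plan has two simple defaults. One uses the stop time as observed, so a quit at 3 minutes scores better than a success at 6. The other drops the failures, so the method is judged only on those who could do it. Either way, the share of new wearers who could not do the method disappears from the comparison.

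Random order does not remove the problem. It balances practice and fatigue across methods, but failure is likely to follow the difficulty of the method itself. At stake is advice to practitioners: a method could be described as quick although a sizeable share of subjects never completed it.

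**Working it through.** **The plan's own figure.** The Subjects and Recruitment section states "25 subjects will be recruited to gain an initial understanding of how subjects prefer to apply SLs", plus 5 for screen failures: 25 + 5 = 30, which reproduces. It also says that "a true sample size calculation is not possible for this project". No power, effect size or SD is given, so nothing further can be reproduced.

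**Inputs.** From the documents: 25 subjects, each trying every method, and a 15-minute limit per method. Assumed, because the documents give no times or success rates: method X has 20 successes at a mean of 6 min and 5 quits; method Y has 25 successes at a mean of 6 min.

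**Formula.** Mean time for X = (successes × success time + quits × time assigned to a quit) / 25. Method Y is 6.0 min throughout.

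| Handling of the 5 failures on X | Calculation | X (min) | X minus Y (min) |
|---|---|---|---|
| As observed, quits at 3 min | (20×6 + 5×3)/25 | 5.4 | −0.6 |
| As observed, quits at 8 min | (20×6 + 5×8)/25 | 6.4 | +0.4 |
| Set to the 15-minute limit | (20×6 + 5×15)/25 | 7.8 | +1.8 |
| Excluded | (20×6)/20 | 6.0 | 0.0 |

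X fails 5/25 = 20% of subjects in every row. The direction depends on when subjects quit: X looks faster only if quits come before the typical success, here 6 min. Later quits still shrink the gap, to 0.4 min at 8 min against 1.8 min with failures at the limit.

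**Varying the number of quits at 3 min.** Two quits: (23×6 + 2×3)/25 = 5.76, an apparent advantage of 0.24 min. Eight quits: (17×6 + 8×3)/25 = 5.04, an advantage of 0.96 min.

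**Simulation.** Assumptions: lognormal times with log-SD 0.6, capped at 15 min; medians of 6 min for the harder method and 5 min for the easier; quits, on the harder method only, uniform between 1 and 4 min; 25 subjects per method, drawn independently; 20,000 runs. The table gives the share of trials in which the harder method has the lower mean time.

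| Quitting on the harder method | Stop times as observed | Failures set to 15 min |
|---|---|---|
| 0% | 16% | 16% |
| 20% | 45% | 1% |
| 30% | 62% | 0.2% |
| 40% | 77% | about 0% |

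These figures describe early quitting only.

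**What a success comparison could show.** With 25 per method, approximate power is 87% for 95% against 60%, 70% for 90% against 60%, and 42% for 90% against 70%. This treats the groups as independent and makes no multiplicity adjustment, so it is only a rough guide to the within-subject design.

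**The case against.** A reader might infer that the plan counts give-up times as application times. The documents do not support that. They say the time is recorded and, separately, that the stop is recorded as an event, so an analyst can identify these attempts. The plan is silent on their use.

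A reader might also infer that the ANOVA is on time. Its outcome is not named. The between-method hypothesis in the Specific Aims concerns preference, and an ease ranking is collected. The only time outcome in a hypothesis is the total over all five methods, which is a separate question. A method a subject could not do can still be ranked as hard, so difficulty is not invisible.

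Nor does the success goal go wholly unaddressed. The Introduction speaks of completing training overall, and Aim 2 turns that into a question about time. Finally, nothing in the documents shows that subjects quit early. They may decline only after encouragement and have up to 15 minutes, so late stops are possible, and timed-out attempts entered at 15 minutes would raise a hard method's mean.

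All of this stands, and it makes the false advantage conditional. It does not close the gap. Means and ANOVA suit a continuous outcome, and besides the ease ranking, time is the main per-method measure collected, so a time comparison is a natural reading. Both simple ways of making it hide failures. The absence of a planned success comparison depends on no assumption about timing.

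**Conclusion.** The concern holds as an omission. Success, decline and time-out are distinguished at Visit 2, but the analysis section compares none of them between methods and sets no rule for the times of unsuccessful attempts.

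The consequence for time is conditional on two choices the plan leaves open: comparing methods on time, and using stop times as observed. Under both, the difficulty of abandoned methods is understated. The order of methods is distorted in favour of the worse one only when quits precede typical successes. In the illustration the difference between X and Y runs from −0.6 to +1.8 min on handling and quit time alone, with 20% failure throughout. All times and failure rates are assumed, so the size in this trial is unknown. This should be corrected before analysis.

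**What to change.** In the Data Collection and Analysis section:

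1. Add success within 15 minutes, yes or no for each method, as a stated outcome. Report the proportion per method with a confidence interval and a within-subject comparison (for example Cochran's Q), labelled descriptive at 25 subjects.
2. State that in any per-method time comparison every failed attempt, declined or timed out, ranks below every success, and that a within-subject rank test is used. A stop time is then never treated as an application time. Ranking also avoids giving failures an arbitrary value such as 15 minutes.
3. Optionally, as exploratory work, relate the number of methods completed to the factors listed in Hypothesis 2.

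The cost is analysis wording, one added descriptive outcome, and a rank-based time comparison where failures occur. Visit 2 already collects the data, so no visit or procedure changes.

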#### *Visit 3: Outcome Visit*

**1. Visual Acuity:** Visual acuity with SLs will be measured with a high-contrast Snellen chart. If the patient is unable to read the 20/40 letters, the investigator will pinhole over the patient's unaided or presenting refractive error correction to determine the subject's visual potential.

**2. SL Evaluation:** The investigator will use a slit-lamp biomicroscope to evaluate the SLs. The subject will be required to have worn their lenses for at least two hours before the study visit. Anterior segment optical coherence tomography (OCT) will also be performed to obtain an accurate central corneal clearance measurement.

**3. Questionnaires:** All subjects will be asked to complete the SPEED, CLDEQ-8, and OCL-QoL questionnaires at the final SL fitting visit. They will also be asked to complete an investigator-designed questionnaire to understand the initial SL wearing experience.

**4. Study Completion:** The subject will be compensated, and the subject will be exited from the study, but they will be encouraged to continue their SL care with their provider.

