### Clinical Protocol

## *Visit 1: Baseline Visit*

**1. Subject History, Eligibility, Informed Consent:** Subjects will be asked to complete an IRB-approved screening survey to verify that they are still eligible for the study. Eligible subjects will be enrolled, consented, and requested to sign a privacy document. All relevant subject history will be gathered via a questionnaire developed by the investigators that asks about the patient's past contact lens and ocular disease history. Non-eligible subjects will be dismissed at this time.

**2. Questionnaires:** All subjects will be asked to complete the Standardized Patient Evaluation of Eye Dryness (SPEED) questionnaire because it is a validated dry eye symptoms questionnaire that asks about the most common dry eye symptoms. Subjects will also be asked to complete the Contact Lens Dry Eye Questionnaire (CLDEQ)-8 because it is a validated instrument that asks about contact lens comfort and coping mechanisms. The Orthokeratology and Contact Lens Quality of Life Questionnaire (OCL-QoL) will also be administered because it assesses the patient's visual quality of life.

**3. Visual Acuity:** Uncorrected and habitually-corrected visual acuity will be measured with a high-contrast Snellen chart. If the patient is unable to read the 20/40 letters, the investigator will pinhole over the patient's unaided or presenting refractive error correction to determine the subject's visual potential.

**4. Manifest Refraction:** The investigator will determine the subject's refractive error with a phoropter, and binocular balance will be performed if best-corrected visual acuity is equal in between eyes. Visual acuity will be recorded as described above in step 3.

**5. Slit-Lamp Biomicroscopy:** The investigator will use a slit-lamp biomicroscope to document normal and/or remarkable findings of the anterior eye structures: eyelids, conjunctiva, and cornea.

**6. Topography:** Topography will be performed with the SMap3D. The device's standard procedure will be followed, and parameters from this measurement will be sent to the manufacturer to help determine the patient's first SL.

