## *Visit 2: Dispense Visit*

**1. Visual Acuity:** Visual acuity with habitual correction will be measured with a high-contrast Snellen chart. If the patient is unable to read the 20/40 letters, the investigator will pinhole over the patient's unaided or presenting refractive error correction to determine the subject's visual potential.

**2. Slit-Lamp Biomicroscopy:** The investigator will use a slit-lamp biomicroscope to document normal and/or remarkable findings of the anterior eye structures: eyelids, conjunctiva, and cornea.

**3. Lens Dispense:** The investigator will orient the patient and apply the ordered SLs to each eye. The investigator will use a slit-lamp biomicroscope and OCT to evaluate the SLs after 30 minutes of lens settling. If the lenses fit acceptably, the patient will undergo application and removal training (based on the randomization order

determined during step 4). If the lenses do not fit acceptably, new lenses will be ordered, and the subject will be scheduled for a follow up visit for after the study lenses arrive.

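### Questionnaires are listed before every eye examination at Visit 1 but after acuity and lens evaluation at Visit 3, so the paired change could include an effect of having just been tested

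*Combined protocol and SAP*

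**What the plan says.** Under Visit 1: Baseline Visit, step 2 reads "All subjects will be asked to complete the Standardized Patient Evaluation of Eye Dryness (SPEED) questionnaire", and the same step adds the CLDEQ-8 and OCL-QoL. The eye examinations are listed after it, beginning with step 3: "Uncorrected and habitually-corrected visual acuity will be measured with a high-contrast Snellen chart".

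Under Visit 3: Outcome Visit, step 1 is "Visual acuity with SLs will be measured with a high-contrast Snellen chart" and step 2 begins "The investigator will use a slit-lamp biomicroscope to evaluate the SLs", with OCT added. The questionnaires follow as step 3: "All subjects will be asked to complete the SPEED, CLDEQ-8, and OCL-QoL questionnaires at the final SL fitting visit".

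Data Collection and Analysis states the comparison: "Paired t-tests will be used to compare questionnaire scores at the final visit to the baseline visit". No comparison group is described for these scores.

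**The concern.** A paired comparison relies on the two measurements being taken under like conditions. As listed, the baseline forms are filled in before any test of the eyes that day. The final forms are filled in after the subject has read a chart through the new lenses and had them examined by the investigator.

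The instruments are self-reports of dryness symptoms, lens comfort and visual quality of life, and subjects know which lenses they are wearing. Answers of this kind could be coloured by a test taken minutes earlier. With no control group, nothing in the analysis could separate such a shift from a change due to the lenses. What is at stake is the interpretation of the questionnaire change only.

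**Working it through.** **1. Listed order at the two visits**

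| | Visit 1 | Visit 3 |
|---|---|---|
| Before the questionnaires | Step 1: history, eligibility, consent | Step 1: acuity with scleral lenses; step 2: slit lamp and OCT |
| Questionnaires | Step 2 | Step 3 |
| After the questionnaires | Step 3 acuity, 4 refraction, 5 slit lamp, 6 topography, 7 trial lens fitting | Step 4: study completion |

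Eye examinations listed ahead of the forms: none at Visit 1, two steps at Visit 3. The mismatch is there on the page.

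**2. Is the numbering a time order?** The documents do not say. Visit 2: Dispense Visit has one exception: the training mentioned in step 3 uses a randomization order "determined during step 4". Elsewhere the numbers read as a sequence. Visit 1 opens with consent and dismisses ineligible subjects at that point. Lens release at Visit 2 follows the training. Visit 3 ends with compensation and exit. Staff working down the Visit 3 list would naturally examine first and hand out the forms afterwards. If the numbering is not binding, the timing of the forms is unspecified and could differ between subjects.

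**3. Size.** The plan gives no effect size, SD, alpha or power for the questionnaires, so it has no figure to reproduce. The following is an illustration under assumed values.

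- Pairs: n = 25, from Subjects and Recruitment ("25 subjects will be recruited to gain an initial understanding of how subjects prefer to apply SLs"). The further 5, making 30, are an allowance for screen failures.
- Test: two-sided paired t-test with n − 1 = 24 degrees of freedom. The 5% level is assumed.
- True lens effect: zero (assumed).
- Shift from having just been tested: δ, in SDs of the change score (assumed; not in the documents).

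The test statistic follows a noncentral t distribution with 24 degrees of freedom and noncentrality λ = δ × √25 = 5δ. The rejection probability is P(|T| > t), where t is the 97.5% point of the central t distribution with 24 degrees of freedom.

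| Assumed δ | λ = 5δ | Rejection probability |
|---|---|---|
| 0 | 0 | 5.0% |
| 0.1 | 0.5 | 7.7% |
| 0.2 | 1.0 | 16.1% |
| 0.3 | 1.5 | 30.2% |

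Any bias of the same size, from whatever source, would give the same figures. They show how sensitive the test is to a small shift, not that a shift exists.

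**The case against.** The case against making much of this is substantial.

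- **Order not binding.** The Visit 3 sentence fixes the visit, not the moment within it, and Visit 2 shows that step numbers are not always chronological. This stands as a caution. It does not remove the point, because nothing in the plan places the Visit 3 forms before the examinations either.
- **No evidence of an effect.** A reader might infer that the change score is in fact contaminated. The documents do not support that: they offer nothing to show that a Snellen chart, slit lamp or OCT moves these scores in either direction. This stands.
- **Weak mechanism.** By Visit 3 subjects have had the lenses for about a week and must have worn them for at least two hours before the visit, so a chart reading tells them little that is new. Visit 3 describes no feedback on fit to the subject, and fit was already judged at Visit 2. This stands, and argues for a small effect if there is one.
- **The percentages.** A reader might take 8%, 16% or 30% as the trial's actual false positive rate. They rest entirely on assumed shifts, and zero is among the possibilities.
- **A larger limitation dominates.** The comparison is uncontrolled and unmasked, so time, expectation and regression to the mean are already inseparable from any lens effect. This is true, but those need a control group to address, whereas the order can be aligned for nothing.
- **Aims untouched.** A reader might infer a threat to the study's conclusions. The Specific Aims concern preferred application method and the time taken to apply and remove lenses. Questionnaire change is in neither aim, and the study describes itself as preliminary.

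**Conclusion.** The point holds as a minor, avoidable weakness. The listed position of the questionnaires differs between the two visits that are compared, and the paired analysis cannot separate an effect of having just been tested from anything else that changed. Whether such an effect exists, how large it is and which way it runs are all unknown from the documents.

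The conclusion assumes that staff follow the listed order at Visits 1 and 3, which is the natural reading but is not stated as a requirement. If they do not, the issue becomes unspecified timing, and the same sentence in the protocol resolves it. The preference and application-time results do not depend on it.

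**What to change.** Make the questionnaires step 1 of Visit 3, ahead of acuity and lens evaluation, and add one sentence saying that at both visits they are completed before that visit's examinations. The forms, the visit and the workload stay the same; the only cost is renumbering the Visit 3 steps. The requirement for prior lens wear already applies before subjects arrive, so it does not conflict with the move.

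The change aligns only the position within the visit. By Visit 3 subjects will still have been through the examinations and training of Visits 1 and 2, and the report should still describe the result as an uncontrolled before-after change. If data have already been collected in the listed order, report the difference as a limitation of the paired comparison.
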